16.2. Definitions of terms

This section was modified with Amendment 3. For details, see Section 15.2.

Acute kidney injury

Acute kidney injury is define according to the VARC-2 definitions (29), following the AKIN Classification (71). The timing for diagnosis of AKI is up to 7 days and subjects who experience AKI should have follow-up renal assessments after 7 days until stabilization.

Acute Kidney Injury (AKIN Classification)

Stage 1	Increase in serum creatinine to 150-199 % (1.50-1.99 x increase compared with baseline) OR increase of > 0.3 mg/dl (> 26.4 mmol/l) OR Urine output < 0.5 ml/kg/h for > 6 but < 12h
Stage 2	Increase in serum creatinine to 200-299% (2.00-2.99 x increase compared with baseline) OR Urine output < 0.5 ml/kg/h for > 12 but < 24h
Stage 3	Increase in serum creatinine to > 300% (> 3 x increase compared with baseline) OR serum creatinine of > 4.0 mg/dl (> 354 mmol/l) with an acute increase of at least 0.5 mg/dl (44 mmol/l) OR Urine output < 0.3 ml/kg/h for > 24h OR Anuria for > 12h Patients receiving renal replacement therapy.

The increase must occur within 48 hours.

Aortic stenosis (AS)

Aortic stenosis (AS) typically refers to a narrowing, stiffening or obstruction of flow at the level of the native aortic valve. The recently released AHA/ACC heart disease guidelines define the stages for AS (33).

Child-Pugh Classification of Severity of Liver Disease (72, 73)

Modified Child-Pugh classification of severity of liver disease according to the degree of ascites, the plasma concentrations of bilirubin and albumin, the prothrombin time, and the degree of encephalopathy.

Parameter	Points assigned		
	1	2	3
Ascites	Absent	Slight	Moderate
Bilirubin, mg/dL	≤ 2	2-3	>3
Albumin, g/dL	>3.5	2.8-3.5	<2.8
Prothrombin time			
- Seconds over control	1-3	4-6	>6
- INR	<1.8	1.8-2.3	>2.3
Encephalopathy	None	Grade 1-2	Grade 3-4

Grade	Points
A: well-compensated disease	5-6
B: significant functional compromise	7-9
C: decompensated disease	10-15

Moderate renal impairment

Kidney damage or glomerular filtration rate (GFR) $< 60 \text{ mL/min}/1.73 \text{ m}^2$ for ≥ 3 months or with estimated creatinine clearance $< 50 \text{ mL/min}$. Kidney damage is defined as pathologic abnormalities or markers of damage, including abnormalities in blood or urine test or imaging studies.

Non-active prostate cancer

No current or planned diagnostic measures, chemotherapy, surgical treatment or a reduced life expectancy.

New-onset atrial fibrillation (NOAF) or new-onset atrial flutter (74)

NOAF or atrial flutter is diagnosed as a common supraventricular arrhythmia that is characterized by an uncoordinated contraction of the atrium. An electrocardiogram (ECG) recording is necessary to diagnose AF or atrial flutter. Any arrhythmia that has the ECG characteristics of AF and lasts sufficiently long for a 12-lead ECG to be recorded, or for at least 30 seconds on a rhythm strip is considered to be either AF or atrial flutter. The therapeutic approach to NOAF (spontaneous conversion, electrical or medical cardioversion, initiation of oral anticoagulation, and rate control), should be considered an AF episode. The diagnosis requires an ECG or rhythm strip and any clinical consequences should be thoroughly documented in the case report form.

CNS	Central nervous system	ML	Maximum partial likelihood method
COPD	Chronic Obstructive Pulmonary Disease	N/A	Not applicable
CRF	Case report form	NI	Non-inferiority
CSP	Clinical study protocol	NOAC	Non-vitamin K oral anticoagulants
DAPT	Dual-antiplatelet therapy	NOAF	New-onset atrial fibrillation
DSMB	Data safety monitoring board	od	Once-daily
DTE	Death or first adjudicated thromboembolic event	OT	On-treatment
DVT	Deep vein thrombosis	PBE	Primary bleeding event
e.g.	Exempli gratia (for example)	PE	Pulmonary embolism
eCRF	Electronic case report form	SAP	Statistical analysis plan
eGFR	Estimated glomerular filtration rate	TAVR	Transcatheter aortic valve replacement
EOT	End-of-treatment	TEE	Transesophageal echocardiogram
et al.	Et alii (and others)	TIA	Transient ischemic attack
etc.	Et cetera (and so on)	TIMI	Thrombolysis in Myocardial Infarction
FAS	Full analysis set	TTE	Transthoracic echocardiogram
H ₀	Null Hypothesis	US(A)	United States (of America)
H ₁	Alternative Hypothesis	VARC	Valve academic research consortium
HR	Hazard ratio	VKA	Vitamin K antagonists
i.e.	Id est (that is)	VRM	Validity Review Meeting

1. Introduction

Calcific aortic valve stenosis (AS) is characterized by an increased thrombogenic and inflammatory profile¹. Long-term oral antithrombotic treatment after transcatheter aortic valve replacement (TAVR) aims to prevent complications, notably ischemic stroke and myocardial infarction (MI) as well as thromboembolism related to deep vein thrombosis, pulmonary embolism, valve thrombosis, or systemic embolism while minimizing bleeding risk. The baseline risk for ischemic and thromboembolic complications is determined by comorbidities such as concomitant coronary artery disease (CAD), which is present in 20–70% of patients eligible for TAVR. Furthermore, in-hospital atrial fibrillation (AF) may occur in about one-third of patients referred for TAVR².

Therefore, dual-antiplatelet therapy (DAPT) is not optimal in targeting the underlying pathophysiological mechanisms in the actual standard of care after TAVR due to severe AS. Rivaroxaban, through the inhibition of the pathways underlying the increased thrombogenicity, may effectively prevent thrombotic complications after TAVR without exposing this elderly³ population to an increased bleeding risk.

Stroke and transient ischemic attack (TIA) are estimated to occur in 5% of patients at 30 days and 10% of patients at 1 year after TAVR, based on the PARTNER cohorts, on the CoreValve trial, and on a large meta-analysis by Athappan et al^{4, 5, 6}. Approximately half of the strokes within 30 days post TAVR occur within the first 24 hours⁷.

The investigation of anticoagulation in the medical management of patients following TAVR is further justified by the fact that the incidence of new-onset atrial fibrillation (NOAF) after TAVR may be underestimated. Dumont and his group reported that one-third of patients with no prior history of AF had NOAF after TAVR and this was associated with a higher rate of stroke/systemic embolism at 30 days and 1 year². Thus, despite the number of mechanisms that may be involved in stroke after TAVR, there is a particularly strong relationship between post procedural AF and stroke occurring after 24 hours suggesting that cardioembolic origin might significantly contribute to stroke after TAVR. Finally, the clustering of thromboembolic risk factors in TAVR populations such as renal impairment (close to 80%), severe chronic obstructive pulmonary disease (COPD) (15%), coronary artery disease (70%), peripheral vascular disease (30%), and moderate to severe mitral regurgitation (30%), could indicate that long-term anticoagulation therapy (beyond 12 months) after TAVR can be of value.

For further information see the Clinical Study protocol 2015-001975-30 version 3.0 dated 17 August 2016 where upon this SAP is based.

2. Study Objectives

2.1 Primary Objective(s)

The aim of this study is to assess whether a rivaroxaban-based anticoagulation strategy, following successful TAVR, compared to an antiplatelet-based strategy, is superior in reducing death or first thromboembolic events (DTE). This comparison is preceded by a non-inferiority test that must be satisfied.

A second aim of this study is to assess the primary bleeding events (PBE) of the rivaroxaban-based strategy, following TAVR, compared to an antiplatelet-based strategy. PBE is defined as the composite of life-threatening, disabling, or major bleeding events and is classified according to the VARC definitions following the BARC classification.

2.2 Secondary Objectives

The secondary efficacy objectives are to compare the effects of the rivaroxaban-based strategy and antiplatelet-based strategy with respect to the net-clinical-benefit, defined as the composite of death or first thromboembolic events and life-threatening, disabling, or major bleeding events classified according to the VARC definitions following the BARC classification.

Whereas the secondary safety objectives are safety criteria with respect to bleeding (Thrombolysis in myocardial infarction [TIMI] major or minor bleeds, International society on thrombosis and haemostasis [ISTH] major bleeding, and BARC 2, 3, or 5 bleeds).

2.3 Other Objectives

Other secondary efficacy and safety objectives are to compare the effects of a rivaroxaban-based strategy and an antiplatelet-based strategy with respect to the individual components of the composite of DTE and of the composite of life threatening, disabling, or major bleeding, respectively.

The effect of rivaroxaban-based strategy, following successful TAVR, compared to an antiplatelet-based strategy, on the mean transaortic valve pressure gradient at 360 days as measured by echocardiography will be assessed as an exploratory study endpoint.

3. Study Design

3.1 Study flow diagram

The study design is detailed in Figure 1 and in section 3.2

[figure not shown]

Figure 1: Study flow diagram.

Successful transcatheter aortic valve replacement (TAVR)

§ The duration of the planned treatment period will depend on the time needed to reach the efficacy cut-off date, i.e. to collect the predefined number of efficacy endpoints or earlier if the event rate is unexpectedly low. The expected duration of the treatment is 720 days but may be adjusted depending upon the rate of subject recruitment and efficacy event rates.

R, randomization; ASA, acetylsalicylic acid; OD, once-daily.

3.2 Study plan

This is an event-driven, randomized, open-label with blinded endpoint evaluation, parallel-group, active-controlled, and multicenter study comparing the efficacy and safety of a rivaroxaban-based strategy versus a standard antiplatelet-based strategy for the prevention of ischemic and thromboembolic complications while minimizing the bleeding risk in subjects who successfully underwent TAVR.

The study is divided into a screening period, a planned treatment period, and an observational post-treatment period.

The screening period begins after TAVR. Subjects who have successfully undergone a TAVR procedure of an aortic valve stenosis (either native or valve-in-valve) are included. All inclusion and exclusion criteria should be reviewed before IC is signed. Subjects with an

ongoing/continued indication for oral anticoagulation at the time of randomization are excluded from this study.

Once IC has been obtained and eligibility has been confirmed, subjects are randomized (1:1), to a rivaroxaban-based strategy or to an antiplatelet-based strategy. Randomization must take place within 1-7 days post-TAVR and before hospital discharge. Stratification by site is performed to ensure balance across potential local differences in treatment practices.

The assigned treatment strategy is implemented after randomization.

In each strategy, one antiplatelet therapy agent is dropped after 90 days. This means that in the rivaroxaban-based strategy, ASA is discontinued after 90 days and rivaroxaban 10 mg is to be continued alone. Whereas, in the antiplatelet-based strategy, clopidogrel must be discontinued after 90 days and ASA is to be continued alone.

Study treatments are continued until the efficacy cut-off date, i.e. when 440 subjects are anticipated to have experienced a positively adjudicated primary efficacy endpoint, when subjects will be transitioned from the assigned strategy to an appropriate therapy, as per the clinical site standard of care. This is anticipated to occur approximately 720 days after the first patient is randomized, but may vary depending on the recruitment rate as well as the on the primary efficacy event rate. One on-site visit will be scheduled for each patient when the efficacy cut-off date is anticipated.

In the event of NOAF, study treatments are changed as follows:

Subjects randomized to rivaroxaban-based strategy: Subjects randomized to the rivaroxaban-based strategy should be switched to rivaroxaban 20 mg once-daily (or 15 mg once-daily dose for moderate renal impairment with eGFR < 50 and ≥ 30 mL/min/1.73m²).

Subjects randomized to antiplatelet-based strategy: Subjects randomized to the antiplatelet-based strategy are switched to treatment with VKA with a target INR 2-3.

In case NOAF is diagnosed within the first 90 days after randomization, ASA 75-100 mg once-daily will be continued in both treatment arms in addition to oral anticoagulation with rivaroxaban 20 mg/ 15 mg once-daily or VKA, respectively. ASA 75-100 mg once-daily will be discontinued at 90 days after randomization and anticoagulation continued alone with rivaroxaban 20 mg/ 15 mg once-daily or VKA, respectively. NOAF subjects remain in the study, the timing of on-site visits and/or phone assessments will be kept unchanged until the efficacy cut-off date when an on-site visit and remaining study closure activities take place.

Subject contacts are planned to take place at least at 30, 90, and 180 days after randomization and from 180 days onward, every 180 days until the efficacy cut-off date is anticipated, and the study medication is stopped. Thirty days after the permanent discontinuation of the assigned study medication, a telephone assessment will be performed.

All randomized subjects should be followed until the efficacy cut-off date.

4. General Statistical Considerations

4.1 General Principles

The statistical evaluation will be performed by using the software package SAS release 9.3 or higher (SAS Institute Inc., Cary, NC, USA).

All variables will be analyzed by descriptive statistical methods. The number of data available and missing data, mean, standard deviation, minimum, maximum, median and quartiles will be calculated for metric data. Frequency tables will be generated for categorical data.

Tabulation of frequencies for categorical data will include all possible categories and will display the number of observations in a category as well as the percentage (%) relative to the respective treatment group. Percentages will be rounded to one decimal place.

In general, these summaries will be calculated separately for each treatment group but jointly for all study centers.

If not stated otherwise, all efficacy and safety analyses will be based on findings as confirmed by the Clinical Event Committee (CEC).

Events occurring on the day of randomization will be considered post-randomization, since the CEC is guided to not confirm events pre-randomization.

The validity of subjects for allocation to various populations and data scopes (FAS, pre-NOAF, post-NOAF and on-treatment) will be assessed during one or more interim and a final Validity Review Meetings (VRM) and decisions will be documented in the Validity Review Report. This SAP might be updated based on the results of the validity review meeting.

All subjects randomized will be analyzed as randomized.

4.2 Handling of Dropouts

A subject who withdraws IC before randomization or who develops a violation of the selection criteria before randomization is defined as a screening failure. No follow-up of screening failures is performed. These screening failures will be excluded from the analyses. Only the number of screening failures and the reason for failure will be presented.

Subjects discontinuing study participation prematurely after the subject has been randomized will not be excluded from the analyses.

4.3 Handling of Missing Data

No imputation of data will be performed, with the following exceptions:

Missing or incomplete AE or efficacy/safety event dates will be imputed according to:

- If only the day is missing the date will be set to first day of the recorded month

- If the day and the month are missing the date will be set to the first of January of the recorded year
- If the imputed date is prior to the date of the randomization the date will be set equal to the date of the randomization

Medication dates used for the Data Scopes (see paragraph 5.2) will not be missing or incomplete, since the Study Drug Exposure form in the eCRF does not allow missing or incomplete start and stop dates.

All other missing or incomplete dates will not be imputed.

All missing or incomplete data will be presented in the subject data listing as they are recorded in the eCRF.

4.4 Interim Analyses and Data Monitoring

No formal interim analysis is planned.

The Data Safety Monitoring Board (DSMB) will assess the benefit and harm given the observed rates of efficacy and safety endpoints at that time. Detailed information on the roles and responsibilities of the DSMB are described in the DSMB charter.

4.5 Data Rules

For event data, the number of days from randomization will be used. For each subject, each assessment (event) will be assigned a study day with respect to the trial reference start date, which is the date of randomization of the subject.

If assessment date is on or after the trial reference start date:

Study Day = Assessment day – trial reference start date +1.

If assessment date before the trial reference start date :

Study Day = Assessment date – trial reference start date.

So Study Day 1 will indicate the event occurred at the same day the randomization was performed, Study Day 2 will indicate the event occurred the day following the day of the randomization and Study Day -1 indicates the day before randomization.

4.6 Validity Review

The results of the validity review meeting will be documented in the validity review report and may comprise decisions and details relevant for statistical evaluation. Any changes to the statistical analysis prompted by the results of the validity review meeting will be documented in an amendment and, if applicable, in a supplement to this SAP.

5. Analysis Sets

5.1 Assignment of analysis sets

Full analysis set (FAS)

This subject set includes all randomized subjects, whether treated or not.

5.2 Data scopes

5.2.1 Data scopes according to intention-to-treat principle (ITT analysis)

Efficacy cut-off date

When the anticipated efficacy cut-off date is set, the sponsor informs each investigational site and all subjects must return to the clinic within 6 weeks in order to have a final assessment. This assessment will coincide with the EOT visit for the subjects under treatment. The efficacy cut-off date is the date when the study treatments are discontinued. This date will be determined by the Executive Committee (see protocol 5.3.3). From this day onwards subjects will be transitioned from the assigned strategy to an appropriate therapy, as per the clinical site standard of care.

Censoring of follow-up in ITT analysis

Censoring of follow-up for patients is on the efficacy cut-off date, or date of last known clinical status collected from Last Clinical Status form, or date of death (by CEC adjudication) whichever comes first.

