8.2. Post-study therapy

After the anticipated efficacy cut-off date is set and an on-site visit is completed, there will be an observation period to follow subjects in the transition from study treatment strategies to an appropriate therapy, as per the clinical site standard of care. This post-study therapy should also be recorded in the eCRF.

9. Procedures and variables

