9.4. Efficacy

The primary efficacy endpoint is death or first adjudicated thromboembolic event (DTE) as described under Section 5.3.1. Pertinent information of all clinical events relating to the primary efficacy endpoint or any of its components will be collected between randomization and the visit scheduled after the anticipated efficacy cut-off date is set, and up to 30 days beyond this visit, irrespective of actual treatment of the subject.

Potential efficacy endpoints are adjudicated by the CEC according to the definitions of the CEC charter (see Section 16.1.1).

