9.6. Safety

The primary safety endpoint is primary bleeding event (PBE) as described under Section 5.3.1 Primary variable(s). Pertinent information of all bleeding episodes requiring medical attention will be collected between randomization and the visit scheduled after the anticipated efficacy cut-off date is set, and up to 30 days beyond this visit, irrespective of actual treatment of the subject.

Potential safety endpoints are adjudicated by the CEC according to the definitions of the CEC charter (see Section 16.1.2).

Three bleeding event scales (i.e. BARC, TIMI, and ISTH) are used to classify bleeding events occurring from randomization until the efficacy cut-off date.

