9.6.1.4. Reporting of SAEs/ AEs

The definition of serious adverse events (SAEs) is given in Section [9.6.1.1](#).

The following detailed rules apply to AE and SAE handling and are provided in [Figure 3](#) below:

- Primary or secondary efficacy endpoints, including all-cause death, have to be recorded on Efficacy Endpoint pages of the eCRF. Only non-cardiovascular (non-CV) death has to be reported as SAE within 24 hours of the investigator’s awareness. All other primary and secondary efficacy endpoints are exempted from expedited reporting.
- All primary and secondary safety endpoints (i.e. bleedings) have to be recorded in the eCRF. Only pericardial bleedings and pulmonary alveolar bleedings/ pulmonary bleedings, which are defined as AEs of special interest (see also Section [9.6.1.6](#)), have to be reported within 24 hours of the investigator’s awareness even if classified as non-serious. All other primary and secondary safety endpoints are exempted from expedited reporting.
- All other events (including complications of efficacy or safety endpoints events) that fulfill the seriousness criteria have to be recorded on the AE page of the eCRF and reported within 24 hours of the investigator’s awareness.

[figure not shown]

- All pregnancies in female study subjects or in female partner of a male study subject as well as endpoints of the pregnancies have to be reported within 24 hours of the investigator's awareness. For pregnancy reports, the Pregnancy Monitoring Forms are to be used.
- Non-serious AEs that lead to permanent study drug discontinuation have to be recorded on the AE page of the eCRF but do not require further reporting. Non-serious AEs which DO NOT lead to discontinuation of study medication DO NOT NEED to be recorded and reported. However, non-serious AEs that the investigator considers of particular concern may be recorded on the AE page of the eCRF to bring them to the attention of the sponsor.
- Of the AEs reported, reportable events (i.e. SUSARs) have to be reported to the competent authorities and to the Independent IECs/IRBs according to legal requirements.

If reported, SAEs occurring after the protocol-defined observation period will be processed by the sponsor according to all applicable regulations.

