5.2.2 Data scope according to on-treatment (OT analysis)

Date of permanent discontinuation of the randomized treatment strategy

Date of permanent discontinuation of the randomized treatment strategy is defined as follows:

For subjects randomized to rivaroxaban-based strategy:

- two days after last known ingestion of study rivaroxaban. This date is derived from study drug exposure form, as are the other medication start/stop dates in this section.

For subjects randomized to antiplatelet-based strategy:

- two days after last known ingestion of clopidogrel, ASA, or VKA (after NOAF only), whichever comes last.

Censoring of follow-up for subjects in OT analysis

Censoring of follow-up for patients is the efficacy cut-off date, the date of last known clinical status or date of permanent discontinuation of the randomized treatment strategy + 2 days, whichever comes first.

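### Endpoints are collected for 30 days beyond close-out, but no planned analysis shows events after treatment stops as a separate window

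*SAP*

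**What the plan says.** **What is collected.** Protocol 8.2 states that after the final visit "there will be an observation period to follow subjects in the transition from study treatment strategies to an appropriate therapy". Under 9.2.3 every subject has a telephone contact 30 days (±7) after the last dose, and efficacy and safety endpoints are asked about at that call. Protocol 9.4 collects efficacy events to the close-out visit "and up to 30 days beyond this visit, irrespective of actual treatment of the subject". Protocol 9.6 sets the same window for bleeding: "Pertinent information of all bleeding episodes requiring medical attention will be collected between randomization and the visit scheduled after the anticipated efficacy cut-off date", with the same 30 days added.

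**What is analysed.**
- ITT (SAP 5.2.1): "Censoring of follow-up for patients is on the efficacy cut-off date, or date of last known clinical status collected from Last Clinical Status form", or death, whichever is first.
- On-treatment (SAP 5.2.2): the cut-off, last known status or "date of permanent discontinuation of the randomized treatment strategy + 2 days, whichever comes first".
- Pre-NOAF and post-NOAF (SAP 5.2.3 and 5.2.4): the cut-off at the latest.
- Bleeding: the main analysis uses the ITT scope (protocol 10.3.7, SAP 6.4.1.1). The BARC, TIMI and ISTH scales "are used to classify bleeding events occurring from randomization until the efficacy cut-off date" (protocol 9.6).

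SAP 6.2 to 6.6 contain no summary of events after treatment stops.

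**When the cut-off falls.** SAP 5.2.1 identifies it with the date on which study treatments are discontinued. Protocol 5.3.3 defines it as the date of the primary completion event (the 440th event, or earlier if the event rate is unexpectedly low). Protocol 9.2.2 keeps each subject on study medication until the individual final visit, within 6 weeks of notification.

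**The concern.** The trial deliberately follows subjects through the change from study treatment to local therapy and asks about endpoints at the end of that period, but the SAP gives those data no place in the results. Every subject still on treatment is moved off it at close-out. What happens after an antithrombotic strategy is stopped bears on its benefit and risk. The transition may also differ between arms. Protocol 3.4 describes standard care as dual and then lifelong single antiplatelet therapy, so one may infer that many control subjects would stay on ASA while most rivaroxaban subjects would change drug class.

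Bleeding is the more time-sensitive part. The primary bleeding endpoint is built from BARC types (SAP 6.4). Read literally, bleeds after the cut-off are collected but not graded, so a bleeding table added after adjudication has closed would mean reopening it.

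The SAE tables do not fill the gap. SAP 6.4.1.3 presents them by MedDRA term rather than adjudicated endpoint. Protocol 9.6.1.4 sends endpoint events to endpoint pages and, apart from non-cardiovascular death, says "All other primary and secondary efficacy endpoints are exempted from expedited reporting"; bleeding endpoints other than two special-interest types are treated likewise.

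**Working it through.** **1. Reproduce the plan's figure (protocol 10.4).** Inputs: 540-day event rates of 33.0% and 26.4%, two-sided 5%, 80% power, 2 × 740 subjects, 360-day accrual, follow-up of 360 to 720 days.
- Hazard ratio = ln(1 − 0.264)/ln(1 − 0.33) = 0.3065/0.4005 = 0.7654, as stated.
- Events (Schoenfeld) = 4 × (1.960 + 0.842)²/(ln 0.7654)² = 4 × 7.849/0.07148 = 439.2, so 440, as stated.

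**2. Daily hazards.** Antiplatelet: 0.4005/540 = 7.42 × 10⁻⁴. Rivaroxaban: 0.3065/540 = 5.68 × 10⁻⁴.

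**3. Event-free subjects at close-out.** With uniform accrual, P(event) = 1 − [exp(−360h) − exp(−720h)]/(360h).
- Antiplatelet: 740 × 0.328 = 242.7 events, so about 497 event-free.
- Rivaroxaban: 740 × 0.263 = 194.4 events, so about 546 event-free.
- Total 437 events, close to the planned 440.

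**4. First primary events in the following window,** at unchanged hazards: event-free × [1 − exp(−h × days)].

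| Window | Antiplatelet | Rivaroxaban | Total |
|---|---|---|---|
| 23 days | 8.4 | 7.1 | 15.5 |
| 30 days | 10.9 | 9.2 | 20.2 |
| 37 days | 13.5 | 11.3 | 24.8 |

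The 30-day total is 20.2/440 = 4.6% of the target. It is an upper-end figure for close-out stops, because it treats every event-free subject as stopping then. The documents give no rate of early discontinuation by which to reduce it.

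**5. Precision.** The 95% CI for a between-arm ratio spans a factor of exp(1.96 × √(1/10.9 + 1/9.2)) ≈ 2.4 either way. If the rivaroxaban hazard doubled after stopping (18.3 against 10.9 events, ratio 1.53), power would be about 21%; if it tripled (27.2 against 10.9, ratio 2.3), about 73%. Both multipliers are assumptions.

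**6. Bleeding.** The current text gives no expected rate. Assuming 6% to 18% at 540 days in both arms and a constant hazard, about 5 to 13 first events would fall in 30 days (about 9 at 12%).

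**7. How much of the window is excluded.** Under the SAP's cut-off, treatment stop and end of analysis coincide, so the whole close-out window is outside. Under the protocol's cut-off it need not be. The anticipated date is set before 400 events, so at least 40 remain. The event rate is about 497 × 7.42 × 10⁻⁴ + 546 × 5.68 × 10⁻⁴ ≈ 0.68 per day, and 40/0.68 ≈ 59 days. Final visits fall within 42 days of the setting. A subject seen by about day 29 would have all 30 days before the 440th event, and one seen on day 42 about 59 − 42 = 17 days.

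**The case against.** The strongest reply is that the plan contains no error here. No objective in protocol 4.1 to 4.3 concerns stopping treatment, and ending the analyses at the cut-off agrees between protocol and SAP. Replacement therapy follows site practice, so a contrast between arms after stopping mixes withdrawal with whatever was given next. The expected numbers are small. All of this stands, and it is why only a descriptive summary is justified.

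A reader might also infer stronger claims that the documents do not support:
- *The trial cannot report events after stopping.* It can. The events are collected, and SAP 4.6 provides for amendments and supplements. What is missing is a planned analysis and, for bleeds, a grading rule that reaches past the cut-off.
- *A difference after stopping would be invisible.* For early stoppers, events before the cut-off count under ITT. The primary efficacy and bleeding endpoints are each planned under both ITT and on-treatment scopes, so comparing the two gives an indirect view, though not a separate window.
- *Endpoint events are exempt from SAE reporting.* Protocol 9.6.1.4 exempts most of them only from expedited reporting. They must still be recorded, and serious complications of endpoint events are reported.
- *Adjudication stops at the cut-off.* Protocol 9.4 and 9.6 put no such limit on the committee's adjudication; only the sentence on the three bleeding scales does.

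**Conclusion.** The gap is real but minor. Endpoint data are purposely collected to 30 days beyond close-out, no planned analysis isolates events after treatment stops, and the bleeding scales are not applied after the cut-off. It does not touch the primary test, the error rate, the sample size or the 440-event target.

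At the planning hazards the close-out window would hold at most about 20 first primary events (about 15 to 25 over 23 to 37 days). This assumes exponential event times, uniform accrual, 2 × 740 subjects, hazards unchanged after stopping and everyone event-free stopping at close-out. That is enough to tabulate by arm and too few for a firm comparison. How many of these events the planned scopes actually exclude cannot be settled until protocol 5.3.3 and 9.2.2 and SAP 5.2.1 agree on how the cut-off relates to the last dose.

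It would be wrong to conclude that the censoring rule of the primary analysis should change. Ending that analysis at the cut-off is sound.

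**What to change.** 1. Keep the primary censoring rule as it is.
2. Reconcile the cut-off definition and its relation to the last dose across protocol 5.3.3, protocol 9.2.2 and SAP 5.2.1.
3. Reconcile the end of the on-treatment scope. Protocol 10.2.2 ends it two days after permanent discontinuation. SAP 5.2.2 already defines the discontinuation date as two days after last intake and then adds two more, which gives four.
4. Add a post-treatment scope to SAP 5.2 and its analysis to SAP 6.5. It should run from the end of the reconciled on-treatment window, so that the two do not overlap, to the 30-day (+7) contact. Report adjudicated DTE, its components and PBE as counts and incidence rates with 95% CIs by arm, with planned and early stops separate. Label it descriptive, with no test: replacement therapy is not standardised, and early stops are not a randomised comparison.
5. Amend the sentence on bleeding scales in protocol 9.6 so that classification runs to the end of that window, and do so before adjudication closes.

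The cost is a SAP paragraph, one more table, grading of bleeds that are already collected, and a slightly longer adjudication close-out.
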